## **3. METHODOLOGY**

Design: Multicentre randomized clinical trial

Reference population: Patients with a diagnosis of moderate-severe COPD treated with inhaled bronchodilators.

Study population: Patients with a diagnosis of moderate and / or severe COPD , with bronchodilator treatment in PC Centers, that meet the criteria for inclusion in the study.

Inclusion criteria: Patients who have been visited at least once last year at the center with diagnosis of COPD (J44), with a moderate airflow limitation (FEV1 between 50% - 80%) or severe airflow limitation(FEV1 between 30 % - 50%), treated with bronchodilators, and who accept to participate in the study.

Exclusion criteria

- Patients only receiving home attention (Z74)
- Patients with mental disorders and / or severe mental disorders that do not allow following the sessions
- Patients diagnosed with asthma, tuberculosis or other chronic respiratory diseases
- Patients receiving chronic home oxygen therapy (OCD).
- Patients with terminal disease.

Sample size and sample procedure: Accepting an alpha risk of 0.05 and a beta risk lower than 0.2 in a bilateral contrast, 182 subjects in the first group and 182 in the second are need to detect a difference equal to or greater than 3.51 Units in the St George's Respiratory Questionnaire. It is assumed that the common standard deviation is 11.33. A follow-up loss of 10% has been estimated. Patients will be contacted by phone, via sms, internet or at office consultation (according to the authorization given to the e-CAP) by offering participation in the study and a visit will be scheduled to explain the study and to obtain the signed informed consent and the collection of data.

The random distribution to the groups will be carried out centrally, through a computer program that generates the random numbers managed by a remote investigator to recruiters. The allocation of each patient will be hidden in an envelope that will be opened when the professional has confirmed that he complies with the selection criteria and the patient has signed the informed consent.

Variables

-Quality related to Health (QVRS) will be measured with specific and standardized self-administered questionnaires, validated by our environment:

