- St. George's Respiratory Questionnaire (SGRQ) 22. It is divided into three subscales: symptoms (eight items), activity (16 items), and impacts (26 items). For each subscale and for the general questionnaire, the scores range from 0 (without deterioration) to 100 (maximum deterioration).

- COPD Assessment Test (CAT) 23. It consists of 8 questions with 5 possible answers valued from 0 to 5 (values close to 0: better health status)

-Pulmonary function: it will be measured with forced spirometry with a bronchodilatation test. According to a FEV1 / FVC ratio <70% and the FEV1 post bronchodilatation, patients will be classified in COPD: MILD FEV1> 80%; MODERATE: 50% - 80%; SEVERE: 30% -50%; VERY SEVERE: <30% 24.

-Dyspnea: Quantified by the modified scale of the Medical Research Council (mMRC) 25. It is part of the BODEx index (26).

-Pronostic: BODEx index (26). This index that can be scored from 1 to 3, depending on the variables: body mass index, FEV1, dyspnea (mMRC25 scale) and severe exacerbations of COPD.

-Anxiety and depression: they will be measured with the Goldberg's anxiety-depression scale (27).

-Hospital admissions in the last year (computerized medical history review).

Independent and confusing variables:

- Socio-demographic variables: age (date of birth), gender and level of studies.

-Date of diagnosis of COPD.

-Phenotype: non exacerbator; asthma- COPD; exacerbator with emphysema; exacerbator with chronic bronchitis (1).

Pharmacological treatment:

-Type of treatment: LABA, LAMA, LAMA + LABA, CI, SABA, SAMA, roflumilast.

-Pharmacological compliance: Assessed by the Morisky-Green test (28) that provides information about the causes of non-compliance. It consists of 4 questions with dichotomous response that must be introduced to the normal conversation with the patient.

Inhalation technique: practical test evaluating step by step the technique according to SEPAR and SEMFYC (29)

Comorbidities: hypertension, diabetes mellitus II, dyslipidaemia, depression and anxiety, joint disorders, cardiovascular disease, cardiovascular risk.

Tobacco: Not Smoker / Smoker / former smokers. Yes smoker or ex-smoker: no packages / year. If you smoke number of cigarettes / day. Nicotine dependence (Fargeström) (30), Motivation for change (Richmond) (31) and Phase of change (Prochaska and DiClemente) (32).

Alcohol: BU/week

Working exposure

Environmental exposure ambiental (contamination, tobacco...)

-Other variables:

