-Degree of participation in the intervention: 1 session/ 2 sessions/ 3 sessions/ ≥ 4 sessions

All the variables studied will be collected at baseline, prior to the intervention, and at 6, 12 and 24 months later, both in the intervention and in the control groups.

The control group will follow the usual treatment and follow-up and a visit will be scheduled to obtain the same variables as the intervention group, on a first visit, and at 6, 12 and 24 months.

Collection of data and sources of information:

Data analysis: Analysis will be carried out by intention to treat basis. All patients who signed their informed consent and who have completed the initial evaluation will be included in the analysis. The descriptive statistics of dependent, confusing and general variables will be calculated, both for the intervention group and for the control group and the homogeneity of the two groups for these variables will be checked at the beginning of the study. In all cases, a bilateral alpha error of 0.05 will be considered and the confidence intervals will be calculated at 95%. A variable will be calculated for each

measurement time (baseline, 6 months post-intervention and 12 and 24 months), which is the difference between the result of SGRQ and the other dependent variables of interest in each cut and the initial value, for each individual. Differences between groups and the confidence intervals of the difference to 95% will be calculated. An analysis of the variance of repeated measures (ANOVA) will be performed to evaluate the differences in time of dependent variables attributable to the effect of the intervention. It will adjust for the possible confusers, comorbidity, other interventions carried out, among others.

Difficulties and limitations of the study: This is a clinical trial in which health professionals who usually see the subject of study can know the group to which the patient belongs. They will "try to preserve masking in some important stages of the study: random allocation, evaluation of the main measures, statistical analysis of the data. On the other hand, the duration of the study can lead to long term loss to follow-up. To ensure the patient's adherence telephone location will be performed (at least three attempts per appointment, if the patient has not indicated that he does not want to participate) when missing the intervention sessions and a quarterly reminder telephone contact.

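### The trial is sized for one SGRQ comparison, but the analysis plan gives three follow-up differences and a repeated-measures ANOVA at 0.05 without saying which decides

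*Combined protocol and SAP*

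**What the plan says.** Section 3, sample size paragraph: the error rates are set by "Accepting an alpha risk of 0.05 and a beta risk lower than 0.2 in a bilateral contrast", and the trial is to "detect a difference equal to or greater than 3.51 Units in the St George's Respiratory Questionnaire". On spread it adds: "It is assumed that the common standard deviation is 11.33". With 10% loss this gives 182 per group. No follow-up time is attached to the 3.51, and the SD is not said to be that of a score or of a change.

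Section 3, Data analysis: a derived variable is defined per "measurement time (baseline, 6 months post-intervention and 12 and 24 months), which is the difference between the result of SGRQ"; baseline is what gets subtracted, and the remaining outcomes are handled the same way. Then: "Differences between groups and the confidence intervals of the difference to 95% will be calculated". Then: "An analysis of the variance of repeated measures (ANOVA) will be performed to evaluate the differences in time of dependent variables". The significance rule for all of it is: "In all cases, a bilateral alpha error of 0.05 will be considered and the confidence intervals will be calculated at 95" per cent.

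The Abstract presents group differences and repeated-measures ANOVA side by side as the means of assessing the intervention. The hypothesis in section 2 lists 6, 12 and 24 months with equal standing.

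No section formally names a primary outcome. Three things point to SGRQ: it alone sizes the trial, quality of life is the only patient outcome in the overall objective, and SGRQ is the only outcome named in the analysis text. Two things point away. Specific objective 2, the one that mentions the clinical trial, does not list quality of life. The Variables list gives CAT as a second quality-of-life measure. SGRQ itself has a general score and three subscales, and the plan does not say which is meant.

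**The concern.** A trial sized for one comparison needs to say which comparison that is. Here at least four SGRQ results are candidates: three follow-up differences and an ANOVA effect. Each can be read at full alpha, and no order is given. At stake are the error rate behind a claim of improved quality of life, which depends on how many routes may support it, and the meaning of the 80% power, which belongs to one specific test of one specific quantity. Neither can be settled soundly once results are known, because any choice made then may reflect them.

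**Working it through.** **Inputs from the sample size paragraph.** Two-sided alpha 0.05; power 80% (beta below 0.2); difference 3.51; SD 11.33; loss 10%; two equal groups. From Data analysis: three follow-up times, each expressed as change from baseline. The baseline change is zero by construction, so it adds no comparison.

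**1. Reproduce the plan's figure.** n per arm = 2 × (1.960 + 0.842)² × (11.33/3.51)² = 163.6. Allowing for loss, 163.6/0.9 = 181.7 (unrounded inputs), so 182. The stated size is that of a single two-sample comparison of means. Expected evaluable: 182 × 0.9 = 163.8 per arm.

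**2. Error if any of the three times counts.** Take three standard normal statistics with common correlation r, and success if any |Z| > 1.96. The rate is 1 − ∫[Φ((1.96 − √r·u)/√(1 − r)) − Φ((−1.96 − √r·u)/√(1 − r))]³ φ(u) du. The documents give no correlation, so r is an assumption. The last column adds a test of the three-time average as a fourth route (simulation, 2 million draws).

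| r | any of three times | plus average-effect test |
|---|---|---|
| 0.3 | 13.6% | 14.4% |
| 0.5 | 12.5% | 13.0% |
| 0.7 | 10.9% | 11.1% |
| 0.8 | 9.8% | 9.9% |
| 0.9 | 8.4% | 8.4% |

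If all four visits are equally correlated at a, two changes from baseline correlate at (a − 2a + 1)/(2(1 − a)) = 0.5, which is the 12.5% row. One named test keeps 5%.

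**3. Power of the two natural choices.** Assume 163.8 evaluable per arm, a constant true difference of 3.51, and 11.33 as the SD of the change.
- One named time: SE = 11.33 × √(2/163.8) = 1.252; 3.51/1.252 − 1.960 = 0.84; power 80%.
- Average over three times: SD = 11.33 × √((1 + 2r)/3); power 97%, 93%, 88%, 85% and 83% at r = 0.3, 0.5, 0.7, 0.8 and 0.9.

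**4. If 11.33 is instead the SD of a score.** The SD of an unadjusted change is 11.33 × √(2(1 − ρ)), where ρ is the baseline-to-follow-up correlation (assumed).

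| ρ | SD of change | power, one time | N per arm for 80% with 10% loss |
|---|---|---|---|
| 0.3 | 13.41 | 66% | 254.4, so 255 |
| 0.5 | 11.33 | 80% | 181.7, so 182 |
| 0.7 | 8.78 | 95% | 109.0, so 110 |

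The three-time average, with all four visits correlated at ρ, has SD 10.95, 9.25 and 7.17 and power 83%, 93% and 99%.

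**The case against.** The strongest defence is that the follow-up differences are only estimates. The plan says they and their intervals will be calculated, while only the ANOVA is said to evaluate differences attributable to the intervention. On that reading there is one inferential test and no multiplicity. This is a fair reading, and the plan does not literally state three tests. But a 95% interval that excludes zero is equivalent to a two-sided 0.05 test, the flat alpha rule covers all cases, and the Abstract gives both approaches the same role. Even on this reading, the plan does not say which ANOVA effect decides, and the sample size was not derived for an ANOVA.

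It can also be said that no any-time success rule is written and that every correlation is assumed. Both are true. A reader might infer that the plan runs at 8% to 14% error. The documents do not support that: the range describes a rule they leave open, not one they adopt.

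A reader might also infer that letting the ANOVA decide would cost a lot of power. That is not supported. Under the assumptions of step 3, a simulated group-by-time F test that includes baseline, with Greenhouse-Geisser correction, has about 80% to 84% power, much like one visit. A group-by-time test restricted to follow-up visits would fare badly against a constant difference, but no section specifies one.

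Finally, the case for SGRQ as primary is an inference. The omission of quality of life from specific objective 2 and the presence of CAT weaken it somewhat, which is a further reason to write the choice down.

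**Conclusion.** The concern holds as a missing decision rule, and it should be fixed. SGRQ is the outcome the trial is sized on, but neither its primary status, nor the deciding time, nor the deciding analysis is stated. The sample size arithmetic is sound for one two-group comparison, so a reader should not conclude that 182 per arm is wrong.

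The size is conditional. With any-time success, two-sided error is about 8% to 14% over assumed correlations of 0.9 to 0.3, and an added average-effect test hardly changes it. With one named test it is 5%. The 80% power applies to a single-visit test only if 11.33 is the SD of the quantity analysed, which the plan does not say. Confidence in the gap itself is high because it depends on no assumed figure.

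**What to change.** Before any outcome data are seen, add to Data analysis: *The single primary endpoint is the SGRQ total (general questionnaire) score. The deciding test, at two-sided alpha 0.05, is [the between-group difference in change from baseline at one named follow-up time / the treatment effect averaged over 6, 12 and 24 months]. The sample size refers to this test.* The sponsor picks the option and, for the first, the time. If the average is chosen, say that 3.51 is the average difference.

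Label the other times, the analysis not chosen, the SGRQ subscales, CAT and all other outcomes as secondary, reported with 95% intervals. In the sample size paragraph, state whether 11.33 is the SD of a score or of a change from baseline.

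Cost: wording only, with N kept at 182 per arm. If defining the SD shows that it is a score SD and a single-visit unadjusted change is to decide, the power should be restated using step 4; that question exists already and is not created by this change. The price is that confirmatory claims at the other times and on the other outcomes are given up.

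### SGRQ and the other outcomes are compared as raw change from baseline, with no prespecified adjustment for the baseline value, which gives up precision at no saving.

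*Combined protocol and SAP*

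**What the plan says.** All of this is in section 3, Methodology. The Data analysis text creates a variable for each measurement time, "which is the difference between the result of SGRQ and the other dependent variables of interest in each cut and the initial value", calculated for each individual. It continues: "Differences between groups and the confidence intervals of the difference to 95% will be calculated". A repeated-measures ANOVA is then run "to evaluate the differences in time of dependent variables attributable to the effect of the intervention".

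On covariates it says only: "It will adjust for the possible confusers, comorbidity, other interventions carried out, among others". The list under Variables headed "Independent and confusing variables" covers sociodemographic data, phenotype, treatment, comorbidities, smoking and exposures. It does not include the baseline value of any outcome.

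For baseline comparability, the plan says that "the homogeneity of the two groups for these variables will be checked at the beginning of the study". The variables concerned include the dependent ones. The plan does not say what follows if the groups differ.

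The sample-size text gives a target difference of 3.51 SGRQ units, 182 patients per group, 10% loss and this SD: "It is assumed that the common standard deviation is 11.33". It does not say whether that is the SD of a score or of a change.

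**The concern.** Subtracting the baseline value fixes its coefficient at 1. When the baseline to follow-up correlation is below 1 and the variances are equal, the best coefficient is rho, so subtraction over-corrects and leaves avoidable noise in the group contrast. Seen conditionally, each SGRQ point of chance baseline difference moves the change-score estimate by (1 - rho) points. This is the same loss viewed another way, not a second one.

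The repeated-measures ANOVA does not remove the problem. Run on change scores, it is a change-score analysis. Run on raw scores with baseline as a time level, its group-by-time contrast of a visit against baseline is, in complete data, the same change-score difference.

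At stake are the width of the confidence interval and the power for the outcome on which the trial is sized. A homogeneity check with no stated consequence, next to an open-ended covariate list, also leaves the decision to adjust for baseline until after the data have been seen.

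**Working it through.** **Inputs from the documents (section 3, sample size).** Difference 3.51; SD 11.33; two-sided alpha 0.05; beta below 0.2; 182 per group; 10% loss.

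**Assumptions.** rho is not in the documents, so a range is shown. Variances at baseline and follow-up are equal unless stated. Every comparison is with a change score that has no other covariates.

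**Step 1: reproduce the plan's figure.** n per group = 2 × (1.960 + 0.842)² × 11.33² / 3.51² = 163.6, so 164. Allowing for 10% loss gives 164/0.9 = 183, or 164 × 1.1 = 181. The stated 182 is reproduced. Evaluable patients: 182 × 0.9 = 163.8 per arm, used below with noncentral-t power.

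**Step 2: variance formulas.** Let sb be the baseline SD and k = SD(follow-up)/SD(baseline).
- Change score: sb²(1 + k² − 2·rho·k)
- ANCOVA: sb²k²(1 − rho²)
- At k = 1 the ratio ANCOVA/change is (1 − rho²)/[2(1 − rho)] = (1 + rho)/2.

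**Step 3: single visit, 11.33 read as the SD of change.** Change-score power is 79.8% and the 95% CI half-width is 1.967 × 11.33 × √(2/163.8) = 2.46 points.

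| rho | variance ratio | ANCOVA power | ANCOVA half-width |
|---|---|---|---|
| 0.4 | 0.70 | 91.6% | 2.06 |
| 0.5 | 0.75 | 89.8% | 2.13 |
| 0.6 | 0.80 | 87.8% | 2.20 |
| 0.7 | 0.85 | 85.8% | 2.27 |
| 0.8 | 0.90 | 83.8% | 2.34 |
| 0.9 | 0.95 | 81.8% | 2.40 |

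**Step 4: 11.33 read as the SD of one score.** For a single visit, SD of change = 11.33√[2(1 − rho)] and ANCOVA residual SD = 11.33√(1 − rho²). For the mean of the three follow-ups with a common rho between all visits, the variances are 11.33² × 4(1 − rho)/3 and 11.33² × (1 − rho)(1 + 3·rho)/3.

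| rho | single visit: change | single visit: ANCOVA | three-visit mean: change | three-visit mean: ANCOVA |
|---|---|---|---|---|
| 0.4 | 72.3% | 86.2% | 87.8% | 98.8% |
| 0.5 | 79.8% | 89.8% | 92.8% | 99.1% |
| 0.6 | 87.8% | 93.8% | 96.9% | 99.6% |
| 0.7 | 95.0% | 97.5% | 99.3% | 99.9% |
| 0.8 | 99.3% | 99.7% | >99.9% | >99.9% |

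The single-visit change score reaches 80% at rho = 0.502. For the three-visit mean there is no shortfall.

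**Step 5: unequal variances, rho 0.4 to 0.8.** With k = 0.8 the variance ratio is 0.54 to 0.64. With k = 1.25 it is 0.84 to 1.00. The gain is nil at rho 0.8 and k = 1.25, because rho × k = 1 and the ANCOVA slope then equals the 1 that subtraction imposes.

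**Step 6: the same loss seen through chance imbalance (score SD 11.33).** SE of the baseline difference = 11.33 × √(2/163.8) = 1.25. A 2-SE imbalance is 2.50 points. It shifts the change-score estimate by (1 − 0.4) × 2.50 = 1.50 points at rho 0.4 and by (1 − 0.8) × 2.50 = 0.50 at rho 0.8, against a target of 3.51.

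**The case against.** The strongest reply is that this improves a sound plan and does not correct an error. The change score is unbiased under randomisation, and the sample size reproduces. If 11.33 is the SD of change, the planned analysis delivers its 80%. A shortfall against the trial's own target needs the other reading of the SD, rho below about 0.50 and a single-visit contrast. At high rho the gain is small: at 0.8 the half-width falls by 0.12 points, and at 0.9 power goes only from 79.8% to 81.8%. All of this stands, and it limits the point to lost precision.

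Three further arguments stand in part:
- The open-ended adjustment list could admit baseline, and covariates related to baseline SGRQ might recover some of the gain. But a list that merely permits baseline does not prespecify it. The figures above should be read as relative to a change score without other covariates.
- A 2-SE imbalance is a tail event, expected in about 5% of trials, and the shift it causes should not be counted on top of the variance loss. Both are correct.
- A longitudinal model that keeps baseline as an outcome with a common mean in both arms has similar efficiency. That is an acceptable alternative form of baseline adjustment. It is not a reason to leave adjustment out.

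**Conclusion.** The concern holds. The plan's group contrast is a change-score contrast on either reading of the ANOVA, and baseline is not prespecified as a covariate. With equal variances and no other covariates, adjustment cuts the variance of the SGRQ contrast by 30% at rho 0.4 and by 10% at rho 0.8, where rho is assumed. Whether power falls below target depends on which SD 11.33 is and on rho, and the documents settle neither. The planned test remains valid. This is a change the sponsor should make, because it costs nothing and, in large samples with 1:1 allocation, cannot lose precision. The figures apply to SGRQ only.

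**What to change.** In the Data analysis text, for SGRQ and each other continuous outcome, specify a model for the 6-, 12- and 24-month values with that outcome's baseline value as a named covariate. This can be ANCOVA at each visit, or a longitudinal model with baseline and baseline-by-visit terms in which only the post-baseline visits are outcome levels. Make the adjustment unconditional, so that it does not depend on the homogeneity check. Keep raw mean change by arm as a descriptive column.

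In the sample-size text, state whether 11.33 is the SD of a score or of a change. Admission counts and the mMRC grade need models suited to their scale.

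The cost is one or two sentences in the analysis section. The analysis already includes only patients with a completed initial evaluation, so no new data are needed.

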## **STUDY PROTOCOL**

### **1. BACKGROUND**

Chronic Obstructive Pulmonary Disease (COPD) is characterized by a chronic progressive air flow limitation which is not reversible and mainly associated with tobacco smoke. It is an illness that can be prevented and treated, with systemic involvement and usually accompanied by comorbidity.(1-7)

In recent years, COPD has been defined not only as a pulmonary obstructive disease but also as a disease with systemic repercussion, and phenotypes have been recognized depending on the clinical presentation. (1-9)

COPD is a public health problem of great magnitude, with high morbidity and mortality and a high health cost. The condition is under-diagnosed and its prevalence is expected to continue to increase. (8-9)

The study of global burden of the disease (Global Burden of Disease Study-GBD-) targeted globally,has detected an increase of people with COPD compared to 1990 of almost 120 million.(10)

In Spain, the IBERPOC study reported a prevalence of COPD of 9.1% among the population aged 40-69 years, with a high level of underdiagnosis: 78.2%. The "EPI-SCAN study" estimates the prevalence in the population of between 40 and 79 years in 10.2% with a 73% underdiagnosis. (11)

The mortality rate of COPD, according to the GBD of the WHO, went from the fourth place in 1990 to the third place in 2010. (10) In Spain, according to data from the Carlos III Health Institute, COPD is the fifth cause of mortality. (12) In Catalonia, according to data from the Department of Health 2009 COPD

is the third cause of death. (13)

COPD is associated with a high cost in both health resource consumption and a loss of quality of life related to health (HRQL). In Spain, according to the Ministry of Health and Consumption-2009, "the estimated direct, indirect and intangible costs of COPD are estimated at 750-1000 million euros / year. The average direct cost per patient is 1,712-3,238 euros / year distributed between 40-45% hospital costs, 35-40% in drugs and 15-25% in diagnostic tests. (14)

In Catalonia, according to the Catalan Health Service-2004, direct costs are estimated at 238.82 million euros / year. It originates 10-12% of the consultations in primary care, 10% of visits to pneumology and is the third cause of hospitalization (more than 12% of patients require patients a hospital admission every year and almost 25% of them an annual consultation. (15).

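### Hospital admissions are to be analysed as change from a sparse baseline-year count, one year at a time; the tests stay valid but give up power that the same record review could supply.

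*Combined protocol and SAP*

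**What the plan says.** The hypothesis in section 2 lists hospital admissions among the main variables, and specific objective 2 names their number as a measure of effectiveness. Section 3 (Variables) places the item ahead of the independent and confounding variables and defines it as "Hospital admissions in the last year (computerized medical history review"), that is, a count over the preceding twelve months. All variables are collected at baseline and at 6, 12 and 24 months.

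The Data analysis text gives one rule. For the SGRQ and the other dependent variables of interest, a variable is formed at each time "which is the difference between the result of SGRQ and the other dependent variables of interest in each cut and the initial value". Between-group differences with 95% confidence intervals follow, and then "An analysis of the variance of repeated measures (ANOVA) will be performed". Adjustment is foreseen for confounders and comorbidity; the baseline value of the outcome is not named. The plan mentions no count model, no cumulative count since randomisation and no allowance for follow-up time.

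The only admission frequency in the document is a background figure for Catalonia in section 1: "more than 12% of patients require patients a hospital admission every year".

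**The concern.** At roughly that frequency, up to about 88% of yearly counts are zero. A single prior-year count then says little about a patient's underlying rate, and subtracting it brings a full year of Poisson variation into the comparison.

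The look-back windows make this worse:

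- **6 months.** A one-year look-back contains about six months before randomisation. These months are also in the baseline count and cancel in the difference, so only half a year of treated time is compared with half a year of untreated time.
- **12 and 24 months.** Each change rests on one follow-up year, although two years of records will be available.

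At stake is a named effectiveness outcome. A real reduction in admissions is more likely to be missed than it need be, with data that the trial collects anyway.

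**Working it through.** **The plan's own figure.** Inputs from section 3: "In all cases, a bilateral alpha error of 0.05 will be considered"; "a beta risk lower than 0.2 in a bilateral contrast"; a "difference equal to or greater than 3.51 Units in the St George's Respiratory Questionnaire"; standard deviation 11.33; 10% loss. Per group, n = 2(1.960 + 0.842)² × 11.33² / 3.51² = 163.56, and 163.56 / 0.9 = 181.7, rounded up to 182. This reproduces "182 subjects in the first group and 182 in the second". It concerns the SGRQ only; no power is stated for admissions. I use 164 evaluable patients per arm.

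**Assumptions not in the document.** Yearly counts are Poisson around a stable patient rate with a gamma distribution: mean μ = 0.15 per year, shape k = 0.7, rate ratio r = 0.6 in both years. The share with at least one admission is 1 − (1 + 0.15/0.7)^(−0.7) = 12.7%, close to the background figure.

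**Formulas.**
- Change in the yearly count: difference μ(1 − r); variance 2μ in controls and μ(1 + r) + μ²(1 − r)²/k in the intervention arm.
- Mean of the 12- and 24-month changes: same difference; variance 1.5μ and μ(1 + r/2) + μ²(1 − r)²/k.
- Count with mean m: variance m + m²/k.
- SE = √[(sum of the two variances)/164], z = difference/SE, power ≈ Φ(z − 1.96).

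**Hand results.**

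| Analysis | Difference | Variances (control, intervention) | SE | z | Power |
|---|---|---|---|---|---|
| Change at 12 or at 24 months | 0.06 | 0.300, 0.245 | 0.058 | 1.04 | 18% |
| Mean of 12- and 24-month changes | 0.06 | 0.225, 0.200 | 0.051 | 1.18 | 22% |
| One-year count, no subtraction | 0.06 | 0.182, 0.102 | 0.042 | 1.44 | 30% |
| 24-month count, no subtraction | 0.12 | 0.429, 0.226 | 0.063 | 1.90 | 48% |

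At 6 months the difference halves to 0.03. The variances are 0.150 and 0.121, so z = 0.74 and power is about 11%.

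**Simulation.** At the same inputs, simulated power was 18% per cut and 23% pooled, against 30% for one year with baseline as covariate and 48% for the 24-month count. A second set used 12% admitted and k = 0.5. It gave 18% per cut and 20-21% for repeated-measures ANOVA, against 44% for a negative binomial model of the 24-month count with baseline as covariate. With all 182 per arm evaluable these became 19% and 19-21%, against 51%. At rate ratio 0.5 and 164 per arm they were 23-26% and 26-29%, against 67%. Type I error of the planned tests was about 3-7%, within simulation error of 5%.

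**Where the gain arises** (12% admitted, k = 0.5, rate ratio 0.6). Dropping the subtraction raises power from about 18% to 28%. Using 24 months raises it to about 41%. The negative binomial model with baseline covariate adds 2-3 points.

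**Higher admission rates.** At μ = 0.35 (24.7% admitted) and rate ratio 0.6, simulated power was 42% pooled against 77%. Over rate ratios 0.5-0.7 and k from 0.2 to 1.0, the planned power as a share of the attainable power was:

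| Admitted per year | Single cut | Repeated-measures ANOVA |
|---|---|---|
| 12% | 0.30-0.47 | 0.36-0.57 |
| 25% | 0.41-0.63 | 0.50-0.70 |
| 35% (rate ratio 0.6, k = 0.5 only) | 0.62-0.68 | 0.69-0.72 |

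**The case against.** The strongest reply has four parts.

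1. **The ANOVA uses several cuts.** The 12-month look-back covers months 0-12 and the 24-month one covers months 12-24, so both years enter. A reader might infer that the plan discards the first year, when the programme is delivered. That is true of the 24-month cut alone, not of the analysis as a whole. This part stands.
2. **A mean difference in counts is legitimate.** A reader might infer that so many zeros make ANOVA invalid. The simulated error rates do not support that, and a plain t-test on the 24-month total comes close to the count model at about 12% admitted. This part also stands: the loss comes from the subtraction and the short window.
3. **The 24-month total relies on a lasting effect.** The programme is 4 to 6 visits 15 days apart, so waning is plausible. With rate ratio 0.6 in year 1 and 1.0 in year 2 (μ = 0.15), simulated power was 14% for the 24-month total against 18% for the planned 12-month change. This tells against making the 24-month total the only analysis. It does not defend the subtraction, since covariate adjustment raised power at every cut where there was a true effect.
4. **The inputs are assumed and the outcome is not the one sized for.** The background figure is a lower bound for another population, and the text does not list which dependent variables are of interest. This limits how firmly the size can be stated. Sections 2 and 3 nevertheless put admissions among the outcomes.

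**Conclusion.** The point holds as a loss of efficiency. Under the stated rule, admissions are analysed validly but with less power than the collected data allow. At about 12-13% admitted per year and an assumed constant rate ratio of 0.6, planned power is about 18% per cut and 20-24% pooled, against 44-50% for the 24-month count.

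A reader might infer that the plan always forfeits more than half the attainable power. The document does not support that: it gives neither the rate ratio nor the dispersion, its admission figure is background, and the retained share rises with the admission rate. Nor does the better analysis make this a well-powered outcome; at rate ratio 0.6 it reaches only about one chance in two. A reader might also extend the point to ordinal measures such as the mMRC grade and BODEx. No loss has been shown for those, and none is claimed here.

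**What to change.** In the Data analysis text of section 3, take hospital admissions, and any exacerbation count, out of the change-from-initial-value rule:

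- Analyse the number of events since randomisation, with the prior-year count as covariate and log follow-up time as offset. A negative binomial model, or Poisson with robust standard errors, gives a rate ratio with its 95% confidence interval.
- Report 0-12 months and 0-24 months, and name in advance which is the main one. The longer window gains power if the effect lasts and loses it if the effect wanes.
- At the 6-month cut, count only events after randomisation.

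The cost is a change of wording. The events come from the same record review, provided that they are extracted with dates; no further patients or visits are needed. The one small drawback is that the result is a rate ratio and not a mean difference.
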